### 10.3.2 Scoring of Patient-Reported Outcomes

The post-randomization, visit-specific, cross-sectional change from baseline-RT,  $x_{t,i}$ , in number of nocturnal voids is defined as the average across the nights in the Voiding Diary corresponding to the single visit. Regarding assigning number of voids for a single night, the following rules are used:

1. Voids less than 5 minutes apart will be collapsed into a single void and the corresponding volumes will be summed to a total volume. Voids on different sides of a time threshold (5 minutes after bed time with the intention to sleep at night, rising in the morning, and 30 minutes after rising in the morning) will not be collapsed.
2. If day/night cannot be assigned due to missing go-to-bed or got-up time, number of nocturnal voids and NUV for that 24-hour period is set to missing.
3. If day/night can be assigned and there are no voids during the night period, number of nocturnal voids is set to 0 for that 24-hour period and NUV is set to 0 plus the volume of the first void within 30 minutes of rising in the morning.
4. If day/night can be assigned, and there are a positive number of voids during both the night period, the number of voids during the night period is used, whether or not the volume of every void is registered. If at least one volume is not registered, NUV is set to missing for that 24-hour period.

The post-randomization aggregated average change from baseline-RT,  $y_{t,i}$ , in number of nocturnal voids is defined as the average of the cross-sectional changes from baseline-RT,  $x_{s,i}$ , across the post-randomization visits up to and including the current visit. If the cross-sectional change from baseline-RT,  $x_{t,i}$ , is missing at a single visit, the corresponding aggregated average change from baseline-RT,  $y_{t,i}$ , will be set to missing.

The aggregated average change from baseline being less or equal to 50% of the baseline-RT number of nocturnal voids,  $z_{50\%,t,i}$ , is derived from the corresponding aggregated average change from baseline in number of nocturnal voids,  $y_{t,i}$ , as  $z_{50\%,t,i} = 1$  if  $y_{t,i}/x_{0,i} \leq -0.5$ , and  $z_{50\%,t,i} = 0$  otherwise.

The visit-specific, cross-sectional responder variables related to number of nocturnal voids (33%, 50%, 60%, 70%, 80%, and 90% reduction from baseline; and 1, 2, and 3 voids reduction from baseline) are derived by categorization of the corresponding  $x_{t,i}$  divided by the baseline-RT number of nocturnal voids,  $x_{0,i}$ .

The percentages of nights with response defined as at most one nocturnal void and complete response (no nocturnal voids), respectively, are derived as the percentage of nights with the specific response among all single, post-randomization nights in the Voiding Diary for which number of nocturnal voids can be derived.

The NUV for a single night is the total urine volume in mL from 5 minutes after bedtime with the intention to sleep including the first void within 30 minutes of rising in the morning. The NUV for a visit is calculated as the average of the single-night values. Aggregated values are derived similarly to the derivation of the aggregated values for number of nocturnal voids.

The FUSP for a single night is calculated as the time in minutes from the time of going to bed to the time of first nocturnal void, or time of awakening if no void occurred. The FUSP for a visit is calculated as the average of the single-night values. Aggregated values are derived similarly to the derivation of the aggregated values for number of nocturnal voids.

The total sleep for a single night is calculated as the time in minutes from the time of going to bed to the time of awakening. The total sleep for a visit is calculated as the average of the single-night values.

The diuresis rate measured in mL/min for a single night is calculated as NUV/total sleep. The diuresis rate for a visit is calculated as the average of the single-night values.

The NPi for a single night is calculated as  $100\% \cdot \text{NUV}/24\text{-hours urine volume}$ . The NPi for a visit is calculated as the average of the single-night values.

The NI Diary outcomes will be scored as described in [Holm-Larsen \(2014\)](#):

The NI Diary Total Score for a single night will be calculated as the sum of the scores for the first 11 questions divided by 44 and multiplied by 100. If any of the single-item scores is missing, the NI Diary Total Score is missing for that single night. The NI Diary Total Score for a visit is calculated as the average of the single-night values. The number of nights on which the NI Diary Total Score for a visit is based will be provided.

The NI Diary Overall Impact Score for a single night will be calculated as the score for the 12th question divided by 4 and multiplied by 100. The NI Diary Overall Impact Score for a visit is calculated as the average of the single-night values. The number of nights on which the NI Diary Overall Impact Score for a visit is based will be provided.

Aggregated values for NI Diary Total Score as well as NI Diary Overall Impact Score are derived similarly to the derivation of the aggregated values for number of nocturnal voids.

The PGI-S and the PGI-I are scored as described in [Viktrup \(2012\)](#):  
 The PGI-I is scored from 1 (*Very much better*) to 7 (*Very much worse*).  
 The PGI-S is scored from 1 (*None*) to 4 (*Severe*).

The Hsu 5-point Likert Bother scale is scored as described in [Hsu \(2015\)](#):  
 The Hsu Bother scale is scored from 0 (*Not at all*) to 4 (*Extremely*).

The ISI will be scored as described in [Bastien \(2001\)](#):  
 For the ISI, each item is scored from 0 (*None/Very satisfied/Not interfering at all/Not at all noticeable/Not at all*) to 4 (*Very severe/Very dissatisfied/Very much interfering/Very much noticeable/Very much*) and ISI is calculated as the sum of the single-item scores. ISI is missing if any single item is missing.

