7 TRIAL ASSESSMENTS

7.1 Assessments Related to Endpoints

7.1.1 e-Diary

Subjects will receive an e-Diary for completion containing: a 3-day voiding diary (Section 7.1.1.1), the NI Diary and PRO questionnaires as described in Section 7.1.1.2. The following items are included in the e-Diary:

- Time of daily IMP administration
- 3-Day Voiding Diary
- Nocturia Impact (NI) Diary[©]
- PRO questionnaires
 - Patient Global Impression of Severity (PGI-S)
 - Patient Global Impression of Improvement (PGI-I)
 - Insomnia Severity Index (ISI)
 - Hsu 5-point Likert Bother Scale

At Visit 1, the subjects will be trained to complete the e-Diary, which they will be encouraged to complete at home for 5 days (Figure 3-2).

If the subject is not able to complete the e-Diary assessments, due to technical issues, prior to Visit 2 (only), it is permitted that the subject repeats the e-Diary assessments.

The e-Diary will be reviewed for completeness by the trial site personnel, via the web portal, throughout the trial.

7.1.1.1 3-Day Voiding Diary

A 3-day voiding diary (included in the e-Diary, Section 7.1.1) will be used to collect information regarding: time of voiding episodes, urine volume, with or without urgency, with or without incontinence and other related information, including time of going to bed and time of awakening in the morning. The subjects will be asked to complete voiding diaries over 3 consecutive 24-hour periods just prior to scheduled visits, as outlined in Table 7-1 and shown in Figure 3-2 and Figure 3-3.

Table 7-1 Timing of Voiding Diary Assessments

Voiding Diary Assessment	3 Consecutive Days Prior to Visit(s)
Time of Going to Bed with the Intention to Sleep	2, 3, 4, 5, 6, 7, 8
Time of Awakening in the Morning	2, 3, 4, 5, 6, 7, 8
Assessment of Urgency and Incontinence Episodes	2
Number and Timing of Nocturnal Voids	6, 7
Number and Timing of Voids during 24-hours	2, 3, 4, 5, 8
Nocturnal Urine Volume	3*
24-hour Urine Volume	2, 4, 5, 8

* Includes collection of total urine volume within 30 minutes of rising (in the morning)

Effort should be made to ensure that the subject fills out the voiding diary (in the e-Diary) on the same weekdays throughout the trial for consistency, e.g., if the first voiding diary (in the e-Diary) is started on a Monday, the subsequent e-Diary should also be started on a Monday (Table 7-2). During the night (the sleep period) before the visit no measurements will be recorded.

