Appendix B. Nocturnal Voids

Voiding diary

1. Do you have any voiding event to report?
 YES
 NO
2. When did the voiding event take place?
----- (format in HH:MM AM/PM)

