### 10.2 Primary Efficacy Endpoint

#### 10.2.1 Primary Analysis

The primary endpoint is the aggregated average of change from baseline-RT in number of nocturnal voids after 12 weeks of treatment, that is, averaged across all post-randomization visits. The objectives of the primary analysis are to establish Proof-of-Concept of FE 201836 and to estimate the dose-response profile of FE 201836. The analyses will be performed on the ITT-RT analysis set.

The overall trial outcome is proof-of-concept evaluated by the posterior probability that 500 µg FE 201836 has superior efficacy as compared to placebo ( $Pr(\mu_{500} < \mu_{Plb}) > 97.5\%$ ) based on a Bayesian analysis of the dose-response profile at Week 12 for the ITT-RT analysis set not including the active comparator desmopressin.

The dose-response profile will be characterized by the posterior estimates of the mean dose-response at each dose,  $\mu_d$ , corresponding to two nocturnal voids at baseline and the mean dose-response contrast versus placebo,  $\Delta_d$ , with their associated 95% credibility intervals. The posterior probabilities  $Pr(\Delta_d < -0.3)$ ,  $Pr(\text{dose } d \text{ is MED})$ , and  $Pr(\text{dose } d \text{ is ED}_{85})$ , will be tabulated. The dose-response curve relative to placebo will also be presented graphically with its 95% credible interval in the plots illustrating the therapeutic window (Section 10.4). No multiplicity adjustment will be performed.

The dose-response profiles are determined using the following model: Let  $x_{t,i}$  denote the observed cross-sectional change from baseline-RT in nocturnal voids (averaged across the nights in the Voiding diary corresponding to the visit) and let  $y_{t,i}$  denote the aggregated average change from baseline for subject  $i$ , averaged across post-randomization visits up to time  $t$  (for visit windows see Section 3.1.5):

$$y_{t,i} = \frac{\sum_{k=1}^t x_{k,i}}{t}, \quad t = 1, 2, 3, 4,$$

where  $t$  denotes the nominal post-randomization time points reflecting Visits 5, 6, 7 and 8, corresponding to Weeks 1, 4, 8, and 12, respectively. The final endpoint,  $y_{4,i}$  is modelled as being an observation of

$$Y_{4,i} \sim N(\beta \cdot (x_{0,i} - 2) + \mu_d, \sigma^2), \quad (1)$$

where  $x_{0,i}$  is the baseline-RT number of nocturnal voids,  $\sigma^2$  is the error variance, and  $\mu_d$  describes the dose-response relationship.  $\mu_d$  is assumed to follow a four-parameter sigmoidal model:

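### SAP 10.3.2 rule 3 scores a night as zero voids even when the 24-hour diary at Visits 4, 5 and 8 holds no void at all, which points to an uncompleted diary

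*SAP*

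**What the plan says.** SAP section 10.3.2 has two rules that decide how a night without a recorded night void is scored.

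- Rule 2 covers nights that cannot be delimited: "due to missing go-to-bed or got-up time, number of nocturnal voids and NUV for that 24-hour period is set to missing".
- Rule 3 covers every other night with no entry in the night period: "If day/night can be assigned and there are no voids during the night period, number of nocturnal voids is set to 0". NUV is then 0 plus the volume of any first void within 30 minutes of rising.

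Rule 3 does not ask for a morning void, a daytime void or any other sign that voids were being entered. Rule 4, for nights with at least one void, contains the unfinished phrase "there are a positive number of voids during both the night period". A second, daytime term may have been lost there, but none is stated.

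The night counts feed several endpoints:

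- **Primary endpoint (SAP 10.2.1).** The visit value is "averaged across the nights in the Voiding diary corresponding to the visit", and the visit values are then averaged over four visits.
- **Complete-response and at-most-one-void endpoints (SAP 10.3.2).** The percentage is taken "among all single, post-randomization nights in the Voiding Diary for which number of nocturnal voids can be derived", so a rule-3 zero is in both numerator and denominator.
- **FUSP (SAP 10.3.2).** A night without a void is given the whole time from bed to awakening.

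Protocol Table 7-1 lists "Number and Timing of Voids during 24-hours" for Visits 2, 3, 4, 5 and 8. For Visits 6 and 7 it lists nocturnal voids only.

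**The concern.** Bed and rise times show that the device was used. They do not show that voids were entered in between. Where only night voids are absent, the documents give no means of telling a void-free night from an unlogged one. Where the diary is meant to capture 24 hours and the whole period is empty, the ambiguity largely goes. The protocol (section 3.5.1) puts daily urine output at about 1,500 mL, so a day with no void at all is not credible. Rule 3 nevertheless gives that period the best possible score.

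Nothing later in the plan removes it. The major deviations in SAP section 4 concern eligibility, treatment received, drug intake, diary timing and prohibited medication. None of the seven sensitivity analyses in SAP 10.2.2 targets unlogged nights. The SAP is stricter elsewhere: one missing item makes the NI Diary Total Score for that night missing, and likewise the ISI.

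At stake are the absolute complete-response and at-most-one-void percentages, NUV and FUSP and, to a lesser degree, the primary contrast.

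**Working it through.** The plan states no figure for this point, so there is nothing to reproduce. The simulated operating characteristics do not depend on the rule.

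**Inputs from the documents.** Three diary nights per visit; four post-baseline visits, so 12 nights; entry at Visit 4 requires a mean of at least 2 voids; minimum-effect threshold 0.3 voids; SD of the final endpoint 0.95.

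**Inputs assumed.** True count on an unlogged night, m = 1 to 2.5. Share of unlogged nights, p = 1%, 3% or 5%, equal in all arms and unrelated to the count. True contrast 0.50. True complete-response share 10%.

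**One false zero in one subject.** The visit mean falls by m/3 and the 12-week average by m/12. With m = 2 these are 2/3 = 0.67 and 2/12 = 0.17. Example with baseline 2.0 and nights 2, 1 and unlogged:
- Rule 3: (2 + 1 + 0)/3 = 1.00, a 50% reduction, so a 50% responder.
- Night set to missing: (2 + 1)/2 = 1.50, a 25% reduction, so not a responder.

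**Equal rates across arms.** Contrast = 0.50 × (1 − p). Complete-response share = 0.10 + 0.90 × p.

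| p | Contrast | Complete-response share |
|---|---|---|
| 1% | 0.495 | 10.9% |
| 3% | 0.485 | 12.7% |
| 5% | 0.475 | 14.5% |

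The contrast loses 0.005 to 0.025 voids, that is 0.005/0.95 = 0.5% to 0.025/0.95 = 2.6% of the SD.

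**Part that can be detected.** Visits 5 and 8 hold 2 × 3 = 6 of the 12 post-baseline nights. With p the same at all visits, at most half of the distortion can be found there. At p = 5% that is at most 0.025 × 6/12 = 0.0125 voids of contrast and about 4.5 × 6/12 = 2.25 points of complete-response share. It is less if some subjects log daytime voids but omit night voids.

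**Unequal rates.** Between-arm bias = (difference in p) × m. To reach 0.3 voids the difference must be 0.3/m: 30 points at m = 1, 20 at 1.5, 15 at 2 and 12 at 2.5.

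**Visit 4.** A false zero lowers baseline and so reduces apparent improvement. A subject with one such night qualifies only if the other two nights total at least 6 voids (3 nights × mean of 2). For nights 3, 3 and unlogged, baseline is 2.0 under rule 3 and 3.0 with the night set to missing.

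**The case against.** A reader might go further and infer that any zero without an explicit confirmation should be dropped, because the diary asks "Do you have any voiding event to report". The documents do not support this. The item appears only in an appendix to the exit-interview protocol, followed by a question on when the event took place. It may be a prompt for entering one event. Nothing says that it is put every night, is mandatory, or leaves a stored NO.

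Requiring it could do more harm than rule 3. Suppose that no NO is stored, placebo has mean 2.0 with 10% true zero nights, and active has mean 1.5 with 25% (all assumed). Dropping the zeros at Visits 6 and 7 gives 2.0/0.90 = 2.22 and 1.5/0.75 = 2.00, a difference of 0.22. Averaged over four visits the contrast is (0.50 + 0.50 + 0.22 + 0.22)/4 = 0.36, worse than the 0.475 above. This objection stands, and it confines the remedy to visits with 24-hour collection.

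A reader might also infer that false zeros manufacture a drug effect. With equal rates they dilute the contrast, and nothing in the documents suggests unequal rates of the size needed to reach 0.3 voids. That stands too.

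Finally, there are safeguards: rule 2, e-Diary training, compliance checks at visits, site review of completeness, central monitoring of void counts, and a blinded review that may add major deviations. They bear on how often the problem occurs. None of them changes how an empty 24-hour period is scored.

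**Conclusion.** The point holds for 24-hour periods with bed and rise times but no logged void at Visits 4, 5 and 8. After baseline these are scored as complete responses with NUV 0 and full-length FUSP, although the diary itself indicates non-completion. An empty period at Visit 4 should not be read as a complete response: that endpoint uses post-randomisation nights only, and the error there runs the other way.

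The effect on proof of concept is small and conservative under equal rates. The absolute complete-response share is more sensitive. Both statements rest on assumed rates, because the documents give neither the frequency of such periods nor the device's entry logic. This is a gap in a derivation rule that should be closed, not a threat to the primary conclusion.

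**What to change.** Amend rule 3 in SAP 10.3.2 before the database is released:

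- **Visits 4, 5 and 8.** Score a night 0 only if at least one other void, first-morning or daytime, is logged in the same 24-hour period. Otherwise set the number of nocturnal voids, NUV and FUSP for that period to missing, and average over the remaining nights.
- **Visits 6 and 7.** Keep rule 3, unless the e-Diary is confirmed to store an explicit nightly no-void answer. If it does, use that answer.
- Complete or delete the dangling wording in rule 4.

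At Visits 4, 5 and 8 the check uses data already collected, and a true void-free night is kept as long as any morning or daytime void was logged. The costs are limited. A few nights become missing. If all three periods at Visit 8 are empty, the subject's final value is imputed under the plan's existing missing-at-random model. Night voids omitted by someone who logs daytime voids remain undetected, and the check differs between visits.

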Table 7-2 Example of Voiding Diary Completion When Visit Planned for Friday

	Monday Day-4	Tuesday Day -3	Wednesday Day-2	Thursday Day-1	Friday Visit Day	Saturday	Sunday
Morning		X	X	X			
Afternoon/ Evening		X	X	Finish voiding diary (in e-Diary) X			
Night	Start voiding diary (in e-Diary) X	X	X				

During the screening period, each subject must complete the 3-day voiding diary to document the severity of nocturia and to confirm the eligibility for the active run-in period. The voiding diary should be completed over 3 consecutive 24-hour periods just prior to Visit 2.

During the 1-week active run-in period, each subject must complete a 3-day voiding diary to document treatment response of $\geq 20\%$ decrease in the nocturnal diuresis (mL/min) that was recorded at Visit 2 and confirm the eligibility. The voiding diary should be completed over 3 consecutive 24-hour periods just prior to Visit 3.

During the 1-week washout period, each subject must complete a 3-day voiding diary to confirm the eligibility for the trial. The voiding diary should be completed over 3 consecutive 24-hour periods just prior to Visit 4.

After randomisation (Visit 4) each subject has to complete four 3-day voiding diaries prior to the scheduled trial visits.

Nocturnal voids are defined as the voids occurring from 5 minutes after bedtime, with the intention to sleep at night, until rising in the morning. The first morning void will not be counted as a nocturnal void even though its volume is included as part of the NUV. The time to first void is defined as the time from bedtime with the intention to sleep until first nocturnal void.

The sponsor will provide the subjects with cups for measuring the urine volume.

Prior to each visit the subjects will receive reminders to complete the e-Diary.

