#### 4 Major Protocol Deviations

The following protocol deviations are considered major in the sense that they lead to exclusion of subject or subject data from the Per Protocol Set (see Section 5.2.2):

- The subject is excluded in case of <2 nocturnal voids (average over 3 diary nights) prior to Visit 2 or Visit 4
- The subject is excluded in case of NPi  $\leq$  33% prior to Visit 2
- The subject is excluded in case of <20% decrease in nocturnal diuresis rate (mL/min) from during active run-in (Visit 2 to Visit 3)
- The subject is excluded in case of maximum voided volume <200 mL prior to Visit 2
- The subject is excluded in case of actual treatment not in accordance with randomized treatment
- Visit-specific data are excluded in case of significant non-compliant treatment administration for the visit. For each visit, this is defined as e-Diary-registered intake of trial medication for less than half of the nights for which number of nocturnal voids could be derived
- The subject is excluded in case of significant non-compliant e-Diary completion at Visit 4 defined as the Voiding Diary filled out more than 1 week before the site visit for Visit 4
- For Visits 6, 7 and 8, visit-specific data are excluded in case of significant non-compliant e-Diary completion at the visit defined as the Voiding Diary completed more than 2 weeks before or after the planned day according to the protocol (28, 56, and 84 days after Visit 4, respectively). For Visit 5, significant non-compliance is defined as the Voiding Diary completed more than 14 days after Visit 4
- Visit-specific data are excluded in case of current treatment with any of the following prohibited medications:
  - Thiazide diuretics [ATC code: C03AA]
  - V2-receptor antagonists/agonists (e.g., vaptans/desmopressin, vasopressin) [ATC code: C03XA/H01BA]
  - Loperamide [ATC code: A07DA03]
  - Botulinum toxin (cosmetic non-urological use is acceptable) [ATC code: J06AA04]
  - Valproate [ATC code: N03AG01]

Serious unforeseen deviations deemed to impact the primary endpoint of the trial may additionally be rated as major protocol deviations by the sponsor on the basis of a blinded review of data before declaration of clean-file and lock of database. The list of major protocol deviations will be detailed and documented in the clean file document prior to database release to the trial statistician.

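### Read literally, the SAP scores a void-free night with no registered morning void as 0 mL of nocturnal urine, when it should be missing

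*SAP*

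**What the plan says.** SAP section 10.3.2 gives numbered rules for scoring a single diary night.

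- **Rule 1** does not allow voids to be merged across the time limits, one of which is 30 minutes after rising. A void at 31 minutes is therefore outside NUV.
- **Rule 2** makes the night's void count and NUV missing, but it is triggered only by an absent bed or rising time.
- **Rule 3** applies when the night can be identified and has no nocturnal void: "NUV is set to 0 plus the volume of the first void within 30 minutes of rising in the morning".
- **Rule 4** applies when the night has one or more nocturnal voids: "If at least one volume is not registered, NUV is set to missing for that 24-hour period".

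Protocol section 7.1.1.1 makes the morning void part of the quantity: "The first morning void will not be counted as a nocturnal void even though its volume is included as part of the NUV". On a void-free night, that void is the whole of NUV.

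The nightly values are then averaged: "The NUV for a visit is calculated as the average of the single-night values". The diuresis rate is built on the same number: "The diuresis rate measured in mL/min for a single night is calculated as NUV/total sleep". NPi is likewise a nightly ratio with NUV on top.

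SAP section 4 also excludes a subject from the Per Protocol set for less than a 20% "decrease in nocturnal diuresis rate (mL/min) from during active run-in (Visit 2 to Visit 3").

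**The concern.** A full night with 0 mL of urine is not credible. When rule 3 returns zero, the morning void was late, was not logged, or had no volume entered. The rules send that loss of information in two directions: an unregistered volume makes NUV missing on a night with voids, but leaves zero on a night without them.

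The zero is not neutral between arms. Entry requires a mean of at least 2 nocturnal voids before Visits 2 and 4, so void-free nights should be uncommon at baseline and change from baseline will not cancel the error. On treatment they are expected: the percentage of nights with no nocturnal void is itself a secondary endpoint. Only such nights can score exactly zero.

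The affected results are:

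- change in NUV (secondary, Bayesian and MMRM, SAP Table 5);
- nocturnal diuresis rate (secondary);
- NPi (exploratory);
- the nocturnal-volume therapeutic window (SAP section 10.4);
- the Per Protocol exclusion at the 20% threshold, and through it sensitivity analysis 2 of the primary endpoint (SAP section 10.2.2).

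**Working it through.** No sample size, power or error rate in the plan depends on this rule, so there is no stated figure to reproduce.

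**Inputs from the documents.** Three diary nights per visit; visit value = mean of nightly values; 20% threshold; 750 mL centring constant and 250 mL scaling factor for NUV (SAP Table 6). The 750 mL is used only as a plausible level.

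**Assumed inputs, not in the documents.** Share of void-free nights p: 20–35% on active, 5–10% on placebo. Share of mornings with a late or unlogged void q: 5–20%, equal across arms. Morning void U on a void-free night: 400 mL. Morning void V on a night with voids: 200–300 mL. Time in bed: 480 min. Illustrative NPi: 40%.

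**1. One subject, no drug effect.**

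- Rule 3 read literally: (750 + 750 + 0)/3 = 500 mL. The change is −250 mL, or −33.3%, one full Table 6 scaling unit.
- With only two evaluable nights: (750 + 0)/2 = 375 mL, or −50%.
- Diuresis rate: 750/480 = 1.56 becomes 500/480 = 1.04 mL/min. NPi: 40% becomes 40 × 2/3 = 26.7%.
- With the night missing instead: (750 + 750)/2 = 750 mL, a change of 0%.
- With one zero in three, a 20% fall is reached even if the other two nights rise to 0.8 × 3/2 = 1.2 times baseline.

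**2. Average bias between arms.** Counting void-free nights only, bias = (p active − p placebo) × q × U.

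- Low: (0.20 − 0.05) × 0.05 × 400 = 3 mL.
- High: (0.35 − 0.10) × 0.20 × 400 = 20 mL.

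If nights with voids also lose a late or unlogged morning void, each arm loses q × [pU + (1 − p)V]. The difference is (p active − p placebo) × q × (U − V).

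- Low: 0.15 × 0.05 × (400 − 300) = 0.75 mL.
- High: 0.25 × 0.20 × (400 − 200) = 10 mL.

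Against Table 6, 20 mL is 20/750 = 2.7% of the centring constant and 20/250 = 8% of the scaling unit. The result scales with its inputs: 40% against 15% void-free nights, q = 20% and U = 600 mL would give 0.25 × 0.20 × 600 = 30 mL before the offset.

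**3. How often a 3-night diary contains a zero.** Probability = 1 − (1 − pq)³. On the placebo inputs it runs from 1 − (1 − 0.0025)³ = 0.75% to 1 − (1 − 0.02)³ = 5.9%.

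**4. The 20% threshold.** Simulation of 400,000 subjects with no drug effect, log-normal nights and assumed night-to-night log-SD of 0.2 / 0.3. The share falling by at least 20% is:

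| Visit 3 night | log-SD 0.2 | log-SD 0.3 |
|---|---|---|
| all three observed | 8.6% | 18.4% |
| one scored 0 | 84.4% | 75.4% |
| one set to missing | 11.4% | 21.9% |

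The middle row is conditional on a zero having occurred. Weighting by step 3, the overall false-pass rate rises by 0.0075 × (75.4 − 18.4) = 0.4 to 0.0588 × (84.4 − 8.6) = 4.5 percentage points.

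**The case against.** **The zero is inferred.** Rule 3 presupposes that the morning void exists; if it does not, a programmer might return missing. That is fair: zero is the literal result of an unaddressed case, not an explicit instruction. But the text says to start from 0 and add, and neither set-to-missing rule reaches the case, so a program that follows it returns zero.

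**Rule 4 concerns a different event**, a logged void without a volume, and its wording is visibly incomplete. This stands in part. The inconsistency is direct for an unregistered volume and only analogous for a late or unlogged void. What rule 4 does with a late morning void is also uncertain, which is why both gross and net bias are shown.

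**Void-free nights on the run-in dose often reflect real response.** This is true. The conditional pass rates show what one zero can do, not how often subjects are misclassified.

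**Enrolment.** A reader might infer that one zero night lets a non-responder into the trial under inclusion criterion 9. The documents do not show this. That criterion is judged at Visit 3 from the e-Diary under the protocol's formula (section 3.5.1), and nothing ties SAP rule 3 to it; the SAP rules are introduced under the post-randomisation void count. For NUV, the Visit 3 diary also specifies "Includes collection of total urine volume within 30 minutes of rising (in the morning"), and sites review diary completeness.

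**Conclusion.** The gap is real and worth closing, but its reach is limited. For an affected subject it is large: one zero in three gives −33% without any drug effect. On average it is probably small: about 1 to 10 mL net, or up to about 20 mL if the loss on nights with voids is ignored. These figures rest on assumed frequencies and volumes that the documents do not give. The direction, towards arms with more void-free nights, assumes a similar late or unlogged share in every arm and, for the net figure, a larger morning void on void-free nights than on others.

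Two stronger readings are not supported. One is that false zeros materially exaggerate the dose-response; no document figure shows this, and the net estimate is at most 10/750 = 1.3% of the centring constant. The other is that 75–84% of non-responders would pass the run-in threshold; that holds only once a zero night has occurred, and the unconditional rise is about 0.4 to 4.5 points.

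The void count is scored separately, so the primary endpoint, futility rules and proof-of-concept are untouched except through the Per Protocol sensitivity analysis.

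**What to change.** In rules 3 and 4, state that if no void volume is registered within 30 minutes of rising, NUV, diuresis rate and NPi for that night are missing, and the visit value is the average of the remaining nights. Use the same derivation at every visit, including the Visit 2 to Visit 3 Per Protocol check. Report the number of affected nights by arm and visit, so that the frequencies assumed above can be replaced by observed ones.

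Substituting the first void after rising, however late, is less suitable. It departs from the protocol's 30-minute definition of NUV and adds daytime urine. It would also treat the two run-in visits differently, because 24-hour volumes are collected for Visit 2 but only nocturnal volume for Visit 3 (protocol Table 7-1).

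The cost is a change of SAP wording and derivation code, and a few nights become missing.
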